- Official title: The effect of warm saline irrigation on the amount of bleeding in impacted mandibular third molar surgery: a split-mouth double-blinded randomized clinical trial
- NCT number: NCT04143373
- Document date: November 1, 2019

Study Protocol and Statistical Analysis Plan

To meet the objectives of this split-mouth double-blinded randomized controlled clinical trial, 20 patients who were candidates for bilateral surgical extractions of mandibular third molars were chosen. The participants were selected based on their attendance in the Department of Oral and Maxillofacial Surgery of Tehran University of Medical Sciences, Tehran, Iran from October to December 2017. The sample size was defined to obtain test powers greater than 95% ($\alpha = 0.05$, $\beta < 0.05$).

Patients were enrolled in this study voluntarily, and the details on the study design were explained to them prior to signing the informed consent agreement. The study design was approved by the Institutional Review Board of Tehran University of Medical Sciences, according to the principles of the Helsinki declaration (thesis #6234) and was registered in <https://clinicaltrials.gov> (Code: NCT04143373).

The Inclusion and Exclusion criteria were defined as follows:

Inclusion criteria

- Being a candidate for bilateral mandibular third molar surgery
- Both mandibular third molars must have a similar inclination to the second molar
- Both mandibular third molars must have same Pell & Gregory's classification, indicating the similar surgical difficulty on both sides.

Exclusion criteria

- Presence of any systemic condition or using any type of medication

- History of allergy to local anesthetic (LA) solutions
- Patients with an active gag reflex, because they are more susceptible to swallow the irrigation solution.
- Pregnant and post-menopause women
- Patients with pericoronitis or any local inflammation

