Since it is easier and less time-consuming for the right-handed surgeon to extract the impacted molar on the right side, all surgeries were performed by one right-handed oral and maxillofacial surgeon. For each patient, the control and the experimental sides were chosen by a table of random numbers. The surgeon was aware of the experimental side, however the outcome assessor who checked the amount of suctioned solution, and the data analyst were blind. In the control side and the experimental side, $25\pm2^{\circ}\text{C}$ and $37\pm1^{\circ}\text{C}$ saline were used for irrigation, respectively. All other variables such as the flap type, number, and type of LA cartridges and suturing method were matched between both sides in each patient.

The total time needed for surgery was measured from the moment of the LA injection until the end of suturing. For each patient only 2 cartridges of lidocaine 2% along with 1:100000 epinephrine were used to block the inferior alveolar (direct technique), lingual and long buccal nerves. The timespan between LA injection and the start of surgery was relatively the same. In case the surgery on one side took a relatively longer time, that case would have been excluded.

The amount of saline for irrigation was precisely measured and patients were asked to prevent swallowing till the end of surgery so that all the solutions and debris were suctioned from the oral cavity. In case the volume of irrigation solution was different between control and experimental sides, compensative amount of saline was poured into the mouth and suctioned to balance the amount of suctioned solutions. Also, it was presumed that in healthy patients who were not on any medications, salivary secretion rates were almost the same between surgeries, so that the difference between the volumes of suctioned solutions were due to the differences in bleeding.

The SPSS (Version 23.0, IBM Corp., 2015, New York, USA) and Independent sample T-test were used to analyze the findings.

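### A split-mouth trial is analysed with an independent-samples t-test, whose standard error, confidence interval and p-value are right only if the two sides of a patient are uncorrelated

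*Combined protocol and SAP*

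**What the plan says.** The opening paragraph of the combined protocol and SAP gives the design: "To meet the objectives of this split-mouth double-blinded randomized controlled clinical trial, 20 patients who were candidates for bilateral surgical extractions". The paragraph on the surgeon and allocation makes the patient the block and the side the randomised unit: "For each patient, the control and the experimental sides were chosen by a table of random numbers". The outcome paragraph interprets the measurement as a contrast between a patient's two operations, presuming that "the difference between the volumes of suctioned solutions were due to the differences in bleeding".

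The last paragraph contains the whole statistical method, the software name and this: "Independent sample T-test were used to analyze the findings". No paired test, analysis of differences or model with a patient term appears anywhere.

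On sample size the plan says "The sample size was defined to obtain test powers greater than 95" per cent, with alpha 0.05 and beta below 0.05. It gives no effect size, standard deviation, correlation, sidedness or assumed test.

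**The concern.** The design and the test contradict each other. An independent-samples t-test on the two conditions treats 20 pairs as 40 unrelated readings.

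The plan gives reasons to expect the two readings of a patient to be alike. They come from the same person and the same surgeon. The inclusion criteria match the teeth on inclination and class, "indicating the similar surgical difficulty on both sides". Anaesthetic, flap and suturing are matched, and saliva is presumed nearly equal. Irrigation volume is also balanced within the patient. If that volume varied between patients and was not subtracted (neither is stated), it would add a further shared component.

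The sign of rho is not certain, however. The plan says "it is easier and less time-consuming for the right-handed surgeon to extract the impacted molar on the right side". If that also affected bleeding, a right-left gap with randomised sides would pull rho down.

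With positive rho, the interval is too wide and a real difference in bleeding may be missed. With negative rho, false positives exceed 5% and the interval under-covers.

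**Working it through.** **Inputs.** From the plan: n = 20 pairs, alpha 0.05, power above 95%, independent t-test. Assumed: two-sided testing, normal data, equal standard deviation (SD) on both sides, complete pairs, and rho from -0.3 to 0.7.

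**1. The plan's own figure.** The power claim cannot be reproduced without an effect size and SD. Solving backwards for 95% power:
- Independent test, 20 per side, normal approximation: (1.960 + 1.645) × √(2/20) = 1.14 single-side SDs. With the noncentral t (38 df) it is 1.17.
- Paired test, noncentral t (19 df): 0.85 SDs of the differences. In single-side SDs this is 0.85 × √(2(1 − rho)): 1.20 at rho = 0, 1.01 at 0.3, 0.85 at 0.5 and 0.66 at 0.7.

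So the stated power is neither confirmed nor refuted.

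**2. Standard error.** The true variance of the mean difference is 2·SD²·(1 − rho)/n. The independent test uses 2·SD²/n. The ratio of the standard error used to the correct one is therefore 1/√(1 − rho). At rho = 0.5 this is 1/√0.5 = 1.41. It equals 1 only at rho = 0.

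**3. Consequences.** Simulation of 400,000 trials per setting, 20 bivariate-normal pairs. The power column fixes the effect at 0.85 SDs of the differences, where the paired test has 95%.

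| rho | SE used / correct SE | Mean 95% CI width, independent / paired | Type I error, independent | Power, independent |
|---|---|---|---|---|
| -0.3 | 0.88 | 0.85 | 8.5% | 97.7% (alpha inflated) |
| 0 | 1.00 | 0.97 | 5.0% | 96.0% |
| 0.1 | 1.05 | 1.03 | 3.9% | 94.9% |
| 0.3 | 1.20 | 1.16 | 2.1% | 91% |
| 0.5 | 1.41 | 1.38 | 0.8% | 82% |
| 0.7 | 1.83 | 1.77 | 0.1% | 55% |

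The paired test held 4.9% to 5.0% type I error throughout. Coverage of the independent 95% interval is 100% minus the type I error: 91.5% at rho = -0.3, 97.9% at 0.3 and 99.9% at 0.7.

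**4. Power at a fixed raw difference.** The table's raw effect shrinks as rho rises, so two fixed effects are also shown (independent v paired):

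| rho | 0.8 single-side SD | 1.17 single-side SD |
|---|---|---|
| 0 | 69% v 67% | 95.0% v 93.9% |
| 0.3 | 72% v 82% | 97.3% v 98.7% |
| 0.5 | 76% v 92% | 98.7% v 99.9% |
| 0.7 | 80% v 99% | 99.7% v 100% |

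**5. Price of pairing.** Error degrees of freedom fall from 38 to 19. At rho = 0 this costs about 1.0, 1.5 and 2.1 points of power where the paired test has 95%, 90% and 80%. At the 95% point the loss is gone by rho of about 0.1.

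**The case against.** - **The power loss depends on the effect chosen.** This stands. If the trial was sized for the test it names, the effect is about 1.17 SD. The independent test then keeps power above 95% at each positive rho in the second table, and the loss is at most about 1.4 points. At 0.8 SD the loss is 10 to 19 points for rho of 0.3 to 0.7. The plan does not say which case applies. Neither choice alters the standard error, interval width or type I error.
- **The likely error is on the safe side.** This is true for false positives: with positive rho a significant result would stand. It does not protect a null result or the reported precision.
- **A negative rho is far-fetched.** Largely fair. The plan calls the right side easier and quicker but does not mention bleeding, and it would exclude a case where one side took relatively longer. Write g for the right-left gap in SDs and τ for the patient share of the variance that remains apart from that gap. Then rho = (τ − g²/4)/(1 + g²/4). Reaching -0.3 needs g = 1.31 with τ = 0, or g = 1.85 with τ = 0.3. The -0.3 row is an extreme bound.
- **The test may have been applied to differences grouped by which side had warm saline.** That would be valid, but nothing in the text says so.
- **A mixed model could serve as the primary analysis.** With complete pairs, a random-intercept model without a side term reproduces the paired t-test when its patient variance estimate is positive. It cannot represent a negative rho. The paired test needs no such condition.

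**Conclusion.** The concern holds and must be fixed. The only inferential method in the plan does not match its design, and every p-value and confidence interval it yields is affected. The likely error is conservative: for rho of 0.3 to 0.7 the standard error is 1.20 to 1.83 times too large and type I error is 2.1% down to 0.1%. An anti-conservative result needs a negative rho, which is possible but less plausible.

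These sizes rest on an assumed rho, normality and equal SDs. That the test is correct only at rho = 0 does not depend on which value is assumed. The estimated mean difference is unaffected with complete pairs.

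**What to change.** Replace the independent-samples t-test in the final paragraph with a paired t-test on the within-patient differences in suctioned volume (control side minus warm side). Report the mean difference with its 95% confidence interval. State the number of complete pairs analysed, since the surgery-time exclusion rule could leave fewer than 20.

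A mixed model with a patient random effect and a right/left term may be added as a sensitivity analysis. It answers the side-difference question and is a different model from the paired test.

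The cost is one sentence and no new data, plus the loss of degrees of freedom shown above, which matters only if rho is near zero or below. The plan is written in the past tense. If the independent test has already been run, re-run the analysis on the existing pairs and disclose the change.
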